## 2.1. Statistical Hypotheses

The primary efficacy objective of this study is to assess the intracranial response (IR) rate in BRAF V600E mutation positive subjects assessed by Investigators using modified RECIST 1.1 criteria for Cohort A:

- Cohort A: 75 Subjects who are treatment-naive for brain metastases, asymptomatic and stable on corticosteroids.

The study is designed to provide evidence to support the null hypothesis,  $H_0$ :  $IRR \leq 35\%$  or to reject it in favor of the alternative hypothesis,  $H_A$ :  $IRR \geq 50\%$  for BRAF V600E mutation-positive subjects in Cohort A.

This hypothesis will be tested using a one-sided test for superiority with  $\alpha=0.05$ . There will be no other testing; therefore, there will be no adjustment of the Type I error for multiple testing.

## 3. STUDY DESIGN

This study will evaluate the safety and efficacy of 4 cohorts, each receiving the same treatment. **Cohort A:** Seventy-five subjects with locally confirmed BRAF V600E cutaneous melanoma with metastases to the brain confirmed by MRI, asymptomatic, without prior local (brain) therapy and ECOG score of 0-1. **Cohort B:** Fifteen subjects with locally confirmed BRAF V600E cutaneous melanoma with metastases to the brain confirmed by MRI, asymptomatic, with prior local (brain) therapy and ECOG score of 0-1. **Cohort C:** Up to fifteen subjects with locally confirmed BRAF V600D/K/R cutaneous melanoma with metastases to the brain confirmed by MRI, asymptomatic, with or without prior local (brain) therapy and ECOG score of 0-1. **Cohort D:** Fifteen subjects with locally confirmed BRAF V600D/E/K or R cutaneous melanoma with metastases to the brain confirmed by MRI, symptomatic, with or without prior local (brain) therapy and ECOG score of 0-2.

Subjects will receive dabrafenib 150 mg twice daily and trametinib 2 mg once daily until evidence of disease progression, death, or unacceptable toxicity. Subjects will be required to meet all eligibility criteria and return to clinic on a monthly basis for clinical, skin and laboratory assessments. Intracranial and extracranial disease will be assessed at baseline, Week 4, Week 8, and every 8 weeks thereafter. After Week 40, disease assessments may be performed every 12 weeks. Response to treatment will be evaluated using modified Response Evaluation Criteria in Solid Tumors (RECIST) version 1.1.

An Independent Data Monitoring Committee (IDMC) will be used in this study.

Protocol-specified guidelines for dose adjustments, interruptions and discontinuation due to adverse events are provided in Protocol Amendment 05, dated 13 July 2016 GlaxoSmithKline Document Number (2013N168437\_07). After discontinuation of study treatment, subjects will remain in the study for follow-up assessments including monthly skin assessments up to 6 months and updates on anti-cancer treatment until death. Subjects who have not died, but are no longer being followed for disease progression or survival are considered to have withdrawn from the study. The study will be completed when either all subjects are dead or lost to follow-up, or all subjects still in follow-up

have had at least 3 years follow-up from the date of first dose of study treatment, whichever is earlier.

## 4. PLANNED ANALYSES

In line with ICH E9 [[European Medicines Evaluation Agency \(CPMP/ICH/3633/96\)](#)], membership of the analysis populations will be determined using the definitions in Section 6 of this RAP.

The primary efficacy analysis will be performed when all subjects in Cohort A have had the opportunity for *three (3)* post baseline disease assessments. At this time the final intracranial response analysis will be performed and an interim analysis of PFS and OS will be provided. The final analysis of PFS, OS, and safety will occur after all subjects have died or are otherwise lost to follow-up or 3 years from the first dose of study treatment, whichever is soonest.

### 4.1. Interim Analyses

There is a formal interim analysis for futility only with a statistical decision rule in this trial. For Cohort A, an interim analysis will take place after 22 subjects have been treated and had the opportunity for at least two disease assessments. The responses used in this interim analysis do not have to be confirmed. At least 8 of the 22 subjects must have an IR (intracranial CR or PR) for the trial to continue. If 7 or fewer subjects have an IR, this is evidence that the null hypothesis is true. If accrual is not complete at the time of the interim analysis, it will continue during this analysis.

An IDMC will review accumulating safety and efficacy data, including the results of the interim review of safety and efficacy and make recommendations to continue, modify, or terminate the study if there are concerns regarding safety. The specific responsibilities, review schedules and composition of the IDMC will be outlined in a separate document, the IDMC charter. The IDMC will review the study results at least once for efficacy and futility. Additional routine reviews of safety data will be scheduled as needed.

### 4.2. Final Analyses

The primary analyses will be performed after all subjects in Cohort A have had the opportunity for *three (3)* post-baseline disease assessments. This analysis will be performed after the database is frozen. After all subjects have died or are otherwise lost to follow-up or 3 years from the first dose of study treatment, whichever is soonest, the End of Study analysis will be performed on the total cumulated safety data and overall survival. This analysis will be performed after the End of Study database is frozen. The displays that will be included in this analysis are listed in Section 14.1.1.

## 5. SAMPLE SIZE CONSIDERATIONS

### 5.1. Sample Size Assumptions

The sample size is based on the hypothesized improvement in intracranial response over study GSK BRF113929 (BREAK-MB) in Cohort A. A 35% intracranial response (IR) is not clinically significant over existing therapies. An intracranial response (IR) of 50% is of clinical significance.

For the primary endpoint cohort (A), 75 BRAF V600E mutation positive subjects will be enrolled. At the time of the primary efficacy analysis, at least 33 subjects with an IR (44%) are required to establish that the evidence does not support the null hypothesis. The sample size is based on a one-sided superiority test of binomial proportions with an overall Type I error rate 0.05 incorporating an interim analysis with the spending function proposed by Lan,(1983) with Pocock Boundary. The null hypothesis in Cohort A will be tested assuming IR of 35% against an IR of 50% using a one-sided test for superiority with  $\alpha=0.05$  and power=82%. There will be no other testing; therefore, there will be no adjustment of the Type I error for multiple testing and the primary endpoint test in the primary analysis will be performed at 5% level.

### 5.2. Sample Size Sensitivity

Table 1 shows statistical power for the test of the null hypothesis in Cohort A under the assumed IR of 35%. It includes statistical power for scenarios where the alternative response rate is lower and higher. All statistical power calculations assume 75 BRAF V600E mutation positive subjects in the Cohort A All Treated Subjects population.

**Table 1 Statistical Power Scenarios with 75 BRAF V600E Mutation Positive Subjects in Cohort A**

IR	Statistical Power
40%	22.9%
45%	53.8%
50%	82.1%
55%	96.2%

### 5.3. Sample Size Re-estimation

Sample size re-estimation is not planned for this study.

## **6. ANALYSIS POPULATIONS**

### **6.1. All Treated Populations**

All subjects who receive at least one dose of study medication will comprise the All Treated subjects (ATS) population.

The V600E population will comprise all BRAF V600E mutation positive subjects in the ATS population.

The V600D/K/R population will comprise all BRAF V600D/K/R mutation positive subjects in the ATS population.

### **6.2. All Enrolled**

The All Enrolled population comprises all subjects who were enrolled regardless of whether they had a dose of study treatment.

### **6.3. Safety Population**

The safety population is the ATS population.

### **6.4. Analysis Datasets**

Primary efficacy analyses will be based on investigator-assessed results in the ATS population. If independent review of efficacy is done, those analysis results will be secondary.

Safety analyses will use the ATS population.

The V600D/K/R population, defined above and identified in the study protocol as a population to be used to report on secondary efficacy endpoints by cohorts, will *not* be used. This change was made to accommodate the small sample size in Cohorts B-D (15 subjects per cohort). Analyses of subgroups of 15 subjects would not generally be meaningful and are not specified *a priori*.

## **7. TREATMENT COMPARISONS**

There are no treatment comparisons. The primary objective will be supported by testing the null hypothesis in Cohort A. The four cohorts will not be compared statistically for any endpoint.

## 7.1. Data Display Treatment

The following treatment descriptors will be used on all applicable displays. Results will be reported by cohort.

Treatment Group		Data Display	Order of Treatment Groups
Code	Description		
A	Dabrafenib+Trametinib	Dabrafenib+Trametinib	n/a

## 8. GENERAL CONSIDERATIONS FOR DATA ANALYSES

Analysis datasets will be created according to CDISC/ADaM standards, and data will be listed and summarized according to GSK Integrated Data Standards Library (IDSL) reporting standards. Formatting for dates, times, and decimal places will follow GSK standards except where specified.

The currently supported versions of SAS, S-Plus software, and TSCG (for figures) will be used to perform all data analyses, generate tables, figures, and listings.

All data in the database will be presented in by-subject data listings.

All data up to the time of study completion or withdrawal from the study will be included in the analysis, regardless of duration of treatment.

As the duration of treatment for a given subject will depend on efficacy and tolerability, the duration of follow-up will vary between subjects. Consequently, there will be no imputation for missing data.

Use the center ID in summaries and listings, as needed. Summary tables and listings will NOT generally be separated by investigator nor will investigator be a factor in any statistical models. Unless otherwise stated, all listings will be sorted by center ID, subject number, cohort, then by visit date.

Unless otherwise stated, continuous variables will be summarized with n, mean, median, standard deviation, minimum and maximum, and categorical variables will be summarized with frequency counts and percentages.

Summaries will be produced by cohort.

All laboratory data will be presented in GSK's standard units for reporting.

"Worst-case post-baseline" values will be derived using scheduled and unscheduled visits.

Planned times relative to study drug dosing will be used in all tables and summary figures.

Generally, only pre-specified planned times will be used in the summaries, statistical analyses and calculations of any derived parameters and unscheduled readings will be listed. However, both unscheduled and scheduled readings will be included in the computation of maximum toxicity and in post-baseline shifts displays for labs and in any listing.

Assessment windows will not be defined for the purpose of classifying measurements obtained outside scheduled assessment times.

Deviations from the analyses in the RAP will be identified in the CSR.

### **8.1. Multicenter Studies**

Data from all participating centers will be pooled prior to analysis. It is anticipated that subject accrual will be spread thinly across centers and summaries of data by center would be unlikely to be informative and will not, therefore, be provided. However, a summary of treated subjects by center will be produced.

### **8.2. Other Strata and Covariates**

In all efficacy analyses, there is no stratification. There are no formal plans for investigating any covariates.

### **8.3. Examination of Subgroups**

There are no formal plans for examining subgroups except reporting adverse events by sex and age groups (<65 years old and  $\geq$  65 years old).

### **8.4. Multiple Comparisons and Multiplicity**

The Type I error rate will not be adjusted for multiplicity in secondary or supporting analyses.

## **9. DATA HANDLING CONVENTIONS**

### **9.1. Premature Withdrawal and Missing Data**

Because study treatment is dependent on the study endpoints (e.g., progression), the length of treatment for each subject will depend on the efficacy and toxicity of the treatment, so the duration of treatment will vary across subjects. Similarly the duration of follow up will also vary. All available time-to-event data will be analyzed using suitable statistical methods; subjects with shorter treatment and follow-up due to the natural history of their disease or medical necessities of the treatment of their disease will not be considered to have missing time-to-event data. For endpoints which determine the percentage of responders, subjects with unknown or missing best overall response will be assumed to be non-responders, and will be included in the denominator when calculating the percentages.

In the event that the study is terminated, all available data will be listed and a review carried out by the study team to assess which statistical analyses are still considered appropriate.

Missing data occurs when any requested data is not provided, leading to blank fields on the collection instrument. These data will be indicated by the use of a “blank” in subject listing displays. Answers such as “Not applicable” and “Not evaluable” are not considered to be missing data and should be displayed as such.

Subjects with the designation of treatment relationship for adverse events (AE)s and serious adverse events (SAEs) missing will have the worst case assumed to impute the relationship: if relationship to study treatment is missing it will be assumed to be “Yes”. There will be no other imputation for missing data other than what’s described in Section 9.2 for partial dates and for missing exposure end dates.

### **9.2. Derived and Transformed Data**

The following sections provide a general description of the derived and transformed variables used to describe and analyze the data. Separate analysis dataset specifications provide full details on all data derivations and transformations including descriptions of core standard algorithms and standard Oncology algorithms. The analysis dataset specifications will clearly communicate the content and source of the datasets supporting the statistical analyses.

#### **9.2.1. Reference dates**

There are three reference dates:

Because age is an eligibility requirement, the reference date for age is the date of screening.

The safety reference date is the treatment start date, and will be used to calculate study day for safety measures.

The efficacy reference date is the treatment start date and will be used to calculate study day for efficacy measures and baseline characteristics (such as time since initial diagnosis), as well as efficacy durations.

### 9.2.2. Study Day for Safety Measures

If the date of interest occurs on or after the safety reference date then the safety study day will be calculated as (date of interest - safety reference date) + 1. If the date of interest occurs before the safety reference date then the safety study day will be calculated as (date of interest – safety reference date). There is no safety study day 0.

### 9.2.3. Study Day for Efficacy

If the date of interest occurs on or after the efficacy reference date then efficacy study day will be calculated as (date of interest - efficacy reference date) + 1. If the date of interest occurs prior to the efficacy reference date then efficacy study day will be calculated as (date of interest – efficacy reference date). There is no efficacy study day 0.

### 9.2.4. Duration and Elapsed Time

Durations (e.g., the duration of an adverse event, duration of exposure, etc.) are calculated as the stop date minus the start date plus one.

For elapsed time (e.g., the time since initial diagnosis):

- If the reference date is on or after the event date, then the elapsed time is the reference date minus the event date + 1.
- If the reference date is before the event date then the elapsed time is the reference date minus the event date.

When reporting time to event (TTE) durations (progression-free survival, duration of intracranial, extracranial, and overall response, overall survival) in months, divide the number of days by 30.4375; to report in weeks divide the number of days by 7; to report in years divide the number of days by 365.25. These algorithms for time to event return decimal numbers, and ignore the actual numbers of days in the months or years between start date and stop date. The "year" used in these algorithms is 365.25 days long, and the "month" is one twelfth of that year.

For converting all other durations (e.g., duration of adverse events, duration of exposure, age) to weeks, months or years use the following:

- To report the duration in weeks, divide the number of days by 7.
- To report the duration in months use:  
 $(\text{YEAR}(\text{stopdate} + 1) - \text{YEAR}(\text{startdate})) * 12 + (\text{MONTH}(\text{stopdate} + 1) - \text{month}(\text{startdate}) - 1) + (\text{DAY}(\text{stopdate} + 1) >= \text{DAY}(\text{startdate}))$
- To report the duration in years use:

`intck('year', startdate, stopdate + 1) - (month(stopdate + 1) < month(startdate) or  
(month(stopdate + 1) = month(startdate) and day(stopdate + 1) < day(startdate)))`

The algorithms above for age and duration return whole numbers for months and years, accurately accounting for the actual numbers of days in the months or years between the start date and the stop date.

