### 12.1. Extent of Exposure

Extent of exposure to dabrafenib and trametinib will be summarized separately.

The duration of exposure to study treatment in months (from first day to last day of treatment) will be summarized. Descriptive statistics including mean, median, standard deviation, minimum, and maximum will be calculated for time on study treatment. Moreover, time on study treatment will be categorized in different time period: <3 months, 3 months to 6 months, >6 months to 12 months and >12 months.

The subject's average daily dose, defined as the cumulative dose divided by the duration of exposure for each subject, will be summarized.

Dose reductions will be summarized by number of reductions and reasons for reductions for dabrafenib and trametinib separately. Dose interruptions will be summarized by number of interruptions, reasons for the interruptions, and interruption duration (days) for dabrafenib and trametinib separately. The mean, standard deviation, median, minimum value, and maximum value will be computed for the duration of interruptions as well as the number and percentage of the interruptions  $\leq 7$ , 8-14, 15-21 and >21 days.

All the dose reductions and dose interruptions will be listed separately.

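### Exposure is converted to completed whole months (SAP 9.2.4) but binned at >6 and >12 months (SAP 12.1), so two of the three cut points act a month late and the mean reads about half a month low

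*SAP*

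**What the plan says.** SAP 9.2.4 has two conversions to months.

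- For PFS, OS and the durations of response it says to "divide the number of days by 30.4375", and adds: "These algorithms for time to event return decimal numbers".
- Everything else takes a calendar formula: "For converting all other durations (e.g., duration of adverse events, duration of exposure, age) to weeks, months or years use the following". Exposure is named in that list. Of this formula the SAP says: "The algorithms above for age and duration return whole numbers for months and years".

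Days are counted inclusively: "Durations (e.g., the duration of an adverse event, duration of exposure, etc.) are calculated as the stop date minus the start date plus one".

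SAP 12.1 then applies the result: "The duration of exposure to study treatment in months (from first day to last day of treatment) will be summarized". It asks for the usual statistics: "Descriptive statistics including mean, median, standard deviation, minimum, and maximum will be calculated for time on study treatment". It also asks for four groups: "<3 months, 3 months to 6 months, >6 months to 12 months and >12 months". Nothing visible in either document exempts exposure from the whole-month rule or says that the groups are formed from days or decimal months.

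**The concern.** The groups in 12.1 are written for a continuous quantity. The upper limits of the second and third groups include exactly 6 and exactly 12 months, and anything beyond belongs in the next group. A variable rounded down to completed months cannot take a value between 6 and 7, so everyone in their seventh month of treatment has the value 6 and stays in the second group. The same happens in the thirteenth month. The first cut is not affected, because a strict less-than-3 condition works correctly on completed months. The table would therefore shift at two of its three cut points, always towards shorter exposure, with nothing in the labels to warn the reader.

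Rounding down also lowers the mean. Exposure will be read next to PFS, which is reported in decimal months, so the two would differ by convention as well as in substance.

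**Working it through.** There is no planned figure to reproduce. The check applies the SAP 9.2.4 rule literally and compares it with days/30.4375, the SAP's own decimal month.

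**Formula.** Let Y1, M1, D1 be the year, month and day of first dose, and Y2, M2, D2 those of the day after last dose. Then

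whole months = 12 × (Y2 − Y1) + (M2 − M1 − 1) + 1 if D2 ≥ D1, or + 0 otherwise.

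**By hand, first dose 10 March 2015**

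- Last dose 25 September 2015, 200 days: 0 + (9 − 3 − 1) + 1 = 6. Decimal value 200/30.4375 = 6.57.
- Last dose 25 March 2016, 382 days: 12 + (3 − 3 − 1) + 1 = 12. Decimal value 382/30.4375 = 12.55.

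**Around the cut points, same start date**

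| Days | Decimal months | Whole months | 12.1 group on decimals | 12.1 group on whole months |
|---|---|---|---|---|
| 91 | 2.99 | 2 | under 3 | under 3 |
| 92 | 3.02 | 3 | 3 to 6 | 3 to 6 |
| 200 | 6.57 | 6 | >6 to 12 | 3 to 6 |
| 213 | 7.00 | 6 | >6 to 12 | 3 to 6 |
| 214 | 7.03 | 7 | >6 to 12 | >6 to 12 |
| 382 | 12.55 | 12 | >12 | >6 to 12 |
| 396 | 13.01 | 12 | >12 | >6 to 12 |
| 397 | 13.04 | 13 | >12 | >12 |

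**All durations.** The rule was run for durations of 1 to 1,095 days, with start dates every third day over two years. Decimal months exceed whole months by 0.49 on average. The groups disagree in three places:

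- 183 to 214 days (6-month cut);
- 366 to 396 days (12-month cut);
- 89 to 91 days, for some start dates only, because calendar months differ in length.

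The exact edge of each range depends on the start date.

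**Share of subjects.** This needs a distribution of exposure, which the documents do not give. Assumption: exponential, capped at 1,300 days, with 200,000 simulated subjects per scenario.

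| Assumed median (months) | Mean, decimal minus whole | Moved at 6-month cut | Moved at 12-month cut | Total | Of 75 | Of 15 |
|---|---|---|---|---|---|---|
| 4 | 0.47 | 5.5% | 1.9% | 7.5% | 5.6 | 1.1 |
| 6 | 0.48 | 5.5% | 2.7% | 8.1% | 6.1 | 1.2 |
| 8 | 0.49 | 4.9% | 2.9% | 7.8% | 5.8 | 1.2 |
| 10 | 0.50 | 4.4% | 2.8% | 7.2% | 5.4 | 1.1 |
| 12 | 0.50 | 3.9% | 2.7% | 6.6% | 5.0 | 1.0 |

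Totals are taken before rounding.

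**What the table would show, assumed median 6 months**

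| Group | Decimal months | Whole months |
|---|---|---|
| under 3 | 29.3% | 29.1% |
| 3 to 6 | 20.5% | 26.1% |
| >6 to 12 | 25.2% | 22.3% |
| >12 | 25.1% | 22.4% |

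The mean in that scenario is 8.62 months on decimals and 8.14 on whole months.

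**The case against.** **Whole months are a disclosed convention.** SAP 9.2.4 sets out both conversions and explains the difference, and the completed-unit count is the same one used for age. This stands: it is not an arithmetic slip, and a mean in completed months is legitimate if labelled so. It does not settle the groups, because the stated rule and the stated cut points do not fit together.

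**The groups may be formed some other way.** SAP 9.2 leaves derivation detail to dataset specifications, and SAP 14.2 leaves layouts to a separate document. Neither is available here, so a programmer might in fact bin on days. That lowers certainty about what would be produced. It does not repair the SAP text, and under SAP 8 a departure from the plan has to be identified in the study report.

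**Nothing depends on it.** This is largely right. The primary test does not use exposure; PFS, OS and duration of response use decimal months; compliance (SAP 10.4) uses days. Exposure-adjusted adverse event rates were removed, according to the SAP's revision list.

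A reader might infer more than the documents support:

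- *A single count over all 120 subjects.* Displays 3.0010 and 3.0011 are by cohort, so a pooled count matches no planned table.
- *The same fault in adverse event durations.* SAP 12.3 gives no month unit and no month cut points for them, so no conflict is shown.
- *A median that is also half a month low.* It would simply be reported at about the completed month below, a loss anywhere from nothing to nearly a month. In the scenarios above, where the assumed medians are whole numbers, it hardly moved.

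**Conclusion.** SAP 9.2.4 and 12.1 are inconsistent for exposure. Followed as written, the group labelled 3 to 6 months holds subjects up to just under 7 months, the next runs from 7 to just under 13, and the group labelled >12 holds only those with 13 or more completed months. The mean is about 0.5 month lower than in decimal months.

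The position of the error follows from the SAP text and the calendar alone. The half-month figure needs only that the fractional month be spread roughly evenly. The shares, about 4 to 6% at the 6-month cut and 2 to 3% at the 12-month cut, rest on the assumed exponential distribution with median 4 to 12 months. In the planned cohorts that is roughly 5 to 6 of 75 in Cohort A and about 1 in each cohort of 15.

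The effect is confined to the two descriptive exposure displays. It is minor, and worth correcting because those tables are due at both the interim and the primary analysis (SAP 14.1.1).

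**What to change.** Preferred: in SAP 9.2.4 move duration of exposure to the decimal conversion, days/30.4375, and state in 12.1 that the existing cut points apply to that value. This corrects both the groups and the mean, and puts exposure on the same scale as PFS.

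Alternative: keep whole months and redefine the groups in 12.1 as <3, 3 to <6, 6 to <12 and ≥12. This corrects the groups apart from a day or two of calendar variation, but leaves the mean about half a month low, so the display should say that it counts completed months.

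The rule for the other durations, including age and adverse event duration, can stay as it is. The cost is one line of SAP text and one derivation, with no new data and no effect on any test.
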